**Implementation:**

Consistent with the UK MRC guidelines, we are collecting the following implementation measures as part of our process evaluation:

Timely access to care: determined by the percentage of patients with hip or knee pain who are assessed within 48 hours of calling for an appointment. Only participants who were invited to participate at the time of calling for an appointment for their hip or knee pain will be included in this analysis. Participants who were invited to participate at the time of an appointment with another primary care provider will not be included.

First contact care by the PT: using the percentage of patients with hip or knee pain in the PT-led primary care arm who visited a PT as their first point of contact for the current episode of hip or knee pain.

Hip and knee pain management provided: visits to the primary care site related to hip and knee pain are being collected from the EHR, along with indicators for the following process measures: education provided; exercises prescribed; psychological interventions provided; referrals made to internal primary care team members; referrals made to external HCPs; medications prescribed, deprescribed, and suggested; diagnostic imaging ordered; notes sent to employers or insurers; messages sent to internal primary care team members; and other interventions provided.

Patient adherence to recommendations: adherence to PT activity and exercise recommendations is being collected at the 3-month follow-up survey. We will also be able to determine if participants accessed community PT as part of each follow-up survey timepoint.

**Qualitative Interviews:**

Qualitative interviews are being conducted with patient participants following an interpretive description approach to explore their experiences with the PT-led model of care for hip and knee pain, and their perspectives towards the model of care. A purposive sampling strategy is being used. We are aiming to recruit 8-12 patients representing diversity in age, gender, race, income, employment status, pain duration and intensity, baseline function, and primary care clinic. We are using the concept of information power to determine sample size adequacy within each group—ending recruitment once sufficient depth and breadth of data have been obtained to meet the study objectives. During the consenting process for the main part of the study, patient participants were asked if they were willing to be contacted for qualitative interviews exploring their experiences and perspectives of the PT-led model of care. Using the purposive sampling approach, agreeable patients are being contacted, approximately 2-3 months after enrollment, to explain the purpose of the interviews, discuss the consenting process and letter of information, and schedule an interview time. At the beginning of the interview, the researcher completing the interview confirms that the participant has read the consent form and answer any questions they may have before obtaining verbal consent.

**Protocol Amendments:** any protocol modifications will be documented through updates to the ClinicalTrials.gov registry and described in the final trial publication. Investigators and participants will be informed as needed, depending on the nature of the changes.

**Data Analysis Plan**

All analyses will be by intention to treat principle. Descriptive statistics will be provided for baseline characteristics and outcomes using means (standard deviation) or medians (interquartile range) for continuous variables and frequencies (percent) for categorical variables. We will compare arms using linear mixed models and generalized estimating equations (GEE) to account for clustering and present the corresponding p-values. Analyses will be performed using SAS, version 9.4 (SAS Institute Inc; Cary, NC).

The estimand for patient health outcomes will be the time-specific patient participant treatment effect, adjusting for clustering by primary care site. The primary outcome (LEFS) will be analyzed using linear mixed regression with restricted maximum likelihood (REML) estimates under the assumption of Missing at Random (MAR), which will allow the use of all available data without the need for multiple imputation. The Kenward-Rogers degrees of freedom correction will be used to account for a small number of clusters. The 12-month timepoint will provide the intervention effect as the adjusted least square mean difference between arms with 95% confidence intervals. Secondary comparisons will be made using adjusted least square mean differences between arms at all intermediate time-points. Fixed effects in the mixed model will include time, intervention group by time interaction (omitting the group main effect), pre-specified covariates associated with hip and knee function (patient participant age, sex, duration of current episode of hip or knee pain, income, highest level of education, and comorbidity score), and primary care site rurality and number of active patients (the covariates from the covariate-constrained allocation procedure). Repeated measures will be modeled using a covariance structure determined by information criteria (AIC/BIC). Clinic site will be included as a random effect to account for site clustering. We will assess for potential risk of bias associated with missing data by comparing the characteristics of those who participated. We plan to carry out a sensitivity analysis for a potential departure of our MAR assumption using a delta-adjusted imputation pattern mixture model approach. This approach will allow us to investigate the robustness of our trial outcomes with regard to the missing values of the LEFS.

We plan a secondary analysis using our primary outcome (LEFS) to compare the proportion of participants who experience a meaningful improvement in each arm (responder analysis). We will define a meaningful change as an improvement of greater than or equal to 9 points on the LEFS (the minimally important change). We will present the proportion of participants who experience a meaningful improvement in each arm and compare, using relative risk, between groups using robust Poisson regression, accounting for clustering. We will use empirical covariance (“sandwich”) bias-adjusted (residual-based) estimators, and apply the Fay and Graubard correction for the small number of clusters.

Pain intensity (NPRS), quality of life (EQ-5D-5L), self-efficacy (PSEQ), catastrophic thinking (PCS), pain-related fear (TSK)-11, and depressive symptoms (PHQ-2) will be analyzed using the same analytic approach as described for our primary LEFS analysis, adjusted for the same covariates. We will use simple mean imputation to fill in missing individual items on surveys as described by Chavance. Patient satisfaction and global rating of change do not include a baseline measure and will be assessed using ordinal logistic regression with random effects and adjusting for the same covariates as above.

Incidence rates for minor adverse events (yes or no) will be calculated using robust Poisson regression and compared by calculating relative risks with confidence intervals using GEE-type robust covariance estimators (PROC GLIMMIX, EMPIRICAL option in SAS) to account for clustering. In our models comparing incidence rates, we will use an exchangeable working correlation matrix, empirical covariance (“sandwich”) bias-adjusted (residual-based) estimators, and the Fay and Graubard correction

to account for small number of clusters. Given that we have only included 14 clusters and adverse events are expected to be rare, we anticipate there may be issues of non-convergence or instability in our models. Should the model for adverse events not converge or demonstrate instability, we would attempt to fit the model using an independent working correlation matrix. If there are still issues of non-convergence or instability, we will reduce the model by removing covariates, beginning with duration of pain and income. Severity and duration of minor adverse events will be presented descriptively. We do not anticipate many, if any, serious adverse events; as such, we plan to present these data descriptively.

Visits with primary care physicians or nurse practitioners, time (days) lost from occupational activities, and assistance required (hours) will be presented as rates and compared by calculating rate ratios using GEE-type covariance estimators with an adjusted Poisson or negative binomial model, accounting for clustering, and assuming an exchangeable working correlation matrix. Incidence rates will be used to present visits to other health professionals within the primary care team, participation in group programs offered by the primary care team, and health care services received outside of the primary care team (medications, diagnostic imaging, walk-in clinic visits, ED visits, specialist physician visits, , hospital admissions, interventional procedures, surgeries, other health provider visits). Comparisons between groups for each of these variables will be made by calculating relative risk using robust Poisson regression. These models will incorporate empirical covariance (“sandwich”) bias-adjusted (residual-based) estimators, and the Fay and Graubard correction due to the small number of clusters. These models will use time as an offset to account for variable follow-up times. All of the healthcare utilization and lost time from occupational activity models will control for the same covariates as the patient health outcomes analyses. Similar to our analyses for adverse events, in the case of model non-convergence or instability, we will attempt to fit the model using an independent working correlation matrix and if the model still does not converge and demonstrate stability, we will reduce the model by removing covariates.

Our cost utility analysis will be carried out from societal (primary) and health payer (secondary) perspectives. We will calculate total costs by multiplying the quantity of resource use by the corresponding unit cost, summing the total cost over each follow-up interval to determine total costs at each follow-up time point as well as across the entire study period. Total and mean costs (overall and at each time point) will be presented by aggregated and disaggregated costs. We will estimate quality adjusted life year (QALYs) for every participant using area under the curve and assuming linear interpolation between assessment time points. Bivariate multilevel modelling, accounting for clustering, will be used to analyze the incremental cost per Quality-Adjusted Life Year (QALY) gained and describe the incremental net benefit at various values of willingness-to-pay. We will model treatment group as a fixed effect and account for site clustering. We will adjust for the same covariates as the primary analyses. We will use a probabilistic sensitivity analysis with Monte Carlo simulations to explore the uncertainty in our cost-effectiveness estimates. The results will be illustrated on cost-effectiveness planes, and cost-effectiveness acceptability curves will be presented to demonstrate the likelihood that the PT-led care model is cost-effective across various willingness-to-pay thresholds.

We also plan a subgroup analysis based on sex for each of our effectiveness outcomes, as recommended in the sex and gender equity in research (SAGER) guidelines. We will include an interaction term with sex and group, and group by time in order to assess this. We will present the data using forest plots and 95% confidence intervals.

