**Inclusion/Exclusion:** All adult ( $\geq 19$  years) patients who sought primary care for their hip or knee pain of any duration at participating sites were invited to meet with the RA to discuss participating in the study. Potential participants were excluded if: they reported not being able to understand, read, and write English; they had known cancer causing their hip or knee pain; or they reported being unable to complete the scheduled follow-up surveys over the one-year study period. The inclusion criteria for primary care sites were to have at least 1,500 rostered patients and two or more family physicians. Those sites that already had physiotherapy services or not enough space to include the physiotherapist were excluded.

**Study Power:** Participants were recruited over a 13-month period at all 14 primary care sites (7 PT-led arm, 7 usual care arm). Our power calculation is based on methods described by Hemming et al. Our sample size calculation is targeted to detect a clinically meaningful mean difference of 9 points on the Lower Extremity Functional Scale (LEFS) using a two-sided alpha of 0.05, assuming a conservative standard deviation of 16, a conservative intracluster correlation coefficient of 0.1, a cluster autocorrelation coefficient of 0.5, an individual autocorrelation coefficient of 0.6, and a coefficient of variation of 0.7. Allowing for an attrition of 20% of patient participants at the 12-month follow-up, we require a sample size of 560 participants to achieve  $>80\%$  power. Pilot work for this study suggested we would recruit 1 patient per week per site; as such, we planned and prepared resources to recruit approximately 728 participants.

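### The primary LEFS model seems meant to give the arms a common baseline mean, but the listed fixed effects do not secure it; with ordinary class coding the 12-month contrast gains nothing from baseline LEFS

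*Combined protocol and SAP*

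**What the plan says.** The Data Analysis Plan fits a linear mixed model by REML in SAS 9.4, with a Kenward-Roger correction and a random effect for site. On the mean structure it says: "Fixed effects in the mixed model will include time, intervention group by time interaction (omitting the group main effect". The covariates added are age, sex, pain duration, income, education, comorbidity score, site rurality and number of active patients. Baseline LEFS is not one of them. The effect is the 12-month difference in adjusted least-squares means.

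Section 2 of the outcome measures (Individual Health and Experience Outcomes) has LEFS collected at baseline, 3, 6, 9 and 12 months. The plan does not say in words that baseline LEFS is one of the modelled responses, that the arms share a baseline mean, or that arm-by-time terms begin at 3 months.

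The Data Analysis Plan uses the same approach for NPRS, EQ-5D-5L, PSEQ, PCS, TSK-11 and PHQ-2. It sets two outcomes apart because "Patient satisfaction and global rating of change do not include a baseline measure".

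Study Power is built to detect a "clinically meaningful mean difference of 9 points", tested two-sided at 5%. The SD is taken as 16, the ICC as 0.1 and the CV of site size as 0.7. For correlation over time the inputs are "a cluster autocorrelation coefficient of 0.5, an individual autocorrelation coefficient of 0.6". The section asks for 560 participants, allowing 20% attrition, for power above 80%.

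**The concern.** Leaving out the group main effect is common shorthand for a longitudinal model in which the arms are constrained to one baseline mean. The omission does not impose that constraint by itself. If the group-by-time term covers all five waves, the group effect is already contained in it, because the group column is the sum of that arm's group-by-time columns. The program runs without warning and returns a 12-month contrast that is not adjusted for baseline. Least-squares means at each visit in SAS point towards class factors, so this is an easy program to write from the text.

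What is at stake is the precision of the primary estimate and its exposure to baseline differences. Patients were enrolled after sites had been allocated, research assistants were not blinded, and the constrained allocation balanced only rurality and number of active patients. A baseline LEFS difference across 14 sites is therefore plausible. Two analysts following the same text could also report different primary estimates.

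**Working it through.** **Inputs, all from Study Power.** 560 × 0.8 = 448 completers; 448/14 = 32 per site; 224 per arm. Total variance is 16² = 256. The site part is 0.1 × 256 = 25.6, which a cluster autocorrelation of 0.5 splits into 12.8 stable and 12.8 site-by-time. The person part is 230.4, which an individual autocorrelation of 0.6 splits into 138.24 stable and 92.16 residual. The 12 df used for the t test (14 sites minus 2) is an assumption; the plan gives no figure.

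**Step 1: what the fixed effects span.** There are two arms and five waves.
- Time plus group-by-time as class factors has rank 10.
- Adding the group main effect leaves the rank at 10, so it is the same model.
- Time plus group-by-time at the four follow-up waves only has rank 9, which is a common baseline mean.

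**Step 2: what baseline is worth.** The correlation of a site's baseline and 12-month means is

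r = (12.8 + 138.24/32) / (25.6 + 230.4/32) = 17.12/32.8 = 0.522.

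Using baseline multiplies the variance by 1 − r² = 0.728. Not using it makes the SE larger by a factor of 1/√0.728 = 1.17.

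**Step 3: the plan's own figure, using baseline.** The design effect with unequal sites is 1 + ((1 + 0.7²) × 32 − 1) × 0.1 = 5.668. The SE without baseline is √(2 × 256 × 5.668/224) = 3.60. With baseline it is 3.60 × √0.728 = 3.07. Power is Φ(9/3.07 − 1.96) = 83%, so the stated figure of more than 80% is reproduced.

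**Step 4: without the constraint.** Power is Φ(9/3.60 − 1.96) = 71%. As the design effect may be too harsh on a mixed model, the comparison was repeated by generalised least squares (GLS) on site-by-visit means, over 400 simulated sets of site sizes with CV 0.7. Mean SEs were 2.73 and 3.20, again a ratio of 1.17.

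| Method, 448 completers | Common baseline | Separate baselines |
|---|---|---|
| Design effect, normal | 83% | 71% |
| Design effect, t with 12 df | 77% | 63% |
| GLS, normal | 91% | 80% |
| GLS, t with 12 df | 86% | 73% |

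**Step 5: more patients.** The planned 728 less 20% is about 582 completers. With separate baselines, power is then 72% (design effect, normal), about 64% (design effect, t), 83% (GLS, normal) and 76% (GLS, t). With 14 sites the design-effect, normal-test figure levels off at about 78% however many patients are recruited.

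These figures take complete data at 12 months for the 448 or 582. They include no gain from the other covariates, since the documents give no R².

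**The case against.** The strongest reply is that the text fixes no coding and points towards the right model. Under class coding the parenthesis about the group main effect does nothing; under a constrained-baseline model it has a clear purpose. The separate handling of outcomes without a baseline suggests that baseline is a response in the LEFS model. That is probably the intent, and under it the power claim stands.

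A reader might infer that the plan is wrong as written and that its power has been lost. The documents do not support that, for three reasons.
- The loss depends on a coding that the plan never states.
- Study Power does not show that its figure depends on baseline. It gives no number of periods and does not say whether the powered effect is at 12 months or an average. Averaging four follow-up visits without baseline gives an SE of 3.60 × √((1 + 3 × 0.522)/4) = 2.88, hence 88% power (normal) or 82% (t, 12 df). The autocorrelations could therefore serve another purpose.
- The numbers do not all cross 80% because of the coding. GLS with a normal test stays at 80% with separate baselines, and the design effect with a t test gives only 77% even with a common baseline.

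It is also fair that a comparison without baseline adjustment keeps its type I error, since chance imbalance is already in the standard error. With missing follow-up, a likelihood analysis would also recover a little from baseline.

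What remains is that probable intent does not specify a primary analysis, and the Introduction says the document should give enough detail to be reproduced.

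**Conclusion.** The point holds in conditional form. The listed fixed effects do not secure a common baseline mean, and baseline LEFS enters nowhere else. Fitted with class factors over all five waves, the primary contrast has an SE about 17% larger, and power is 11 to 14 percentage points lower across the four calculations. Both t-based figures at 448 completers are then below 80%. With arm-by-time terms at follow-up only, none of this loss occurs.

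The size rests on the plan's own SD, ICC, autocorrelations and CV, on complete 12-month data for 448 completers, on 12 df where a t test is used, and on no gain from the other covariates. The consequence is lower precision and greater exposure to chance or recruitment-related baseline imbalance. It is not an inflated type I error and not a demonstrated loss of the stated power. This is a free improvement to make before analysis starts.

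**What to change.** Add a sentence to the Data Analysis Plan saying that baseline LEFS is one of the modelled responses, that the arms share one baseline mean, and that arm-by-time terms exist only at 3, 6, 9 and 12 months. In code, set arm to control for every participant at the baseline wave, or use explicit post-baseline indicators. The alternative is to model the four follow-up waves only, with baseline LEFS and baseline LEFS by time as covariates.

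Apply the same choice to NPRS, EQ-5D-5L, PSEQ, PCS, TSK-11 and PHQ-2, each with its own baseline.

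The cost is a sentence of text and about a line of code. No new data are needed, and because the plan starts analysis only after data collection ends, the change can be recorded before any outcome is compared.

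### The trial is sized on a cluster autocorrelation of 0.5 but the primary LEFS model names only a site random effect; at the planning values type I error at 12 months is about 43% (baseline constrained equal) or 11% (baseline free)

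*Combined protocol and SAP*

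**What the plan says.** The Study Power paragraph in Methods sets out to "detect a clinically meaningful mean difference of 9 points on the Lower Extremity Functional Scale (LEFS") with SD 16, ICC 0.1, and "a cluster autocorrelation coefficient of 0.5, an individual autocorrelation coefficient of 0.6, and a coefficient of variation of 0.7". It requires 560 participants at 14 sites, allowing 20% attrition, for more than 80% power.

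The Data Analysis Plan specifies a REML linear mixed model for LEFS, with the 12-month adjusted difference as the primary contrast:

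- Fixed effects: "Fixed effects in the mixed model will include time, intervention group by time interaction (omitting the group main effect"), plus participant covariates, site rurality and number of active patients. Baseline LEFS is not in the covariate list.
- Participant level: "Repeated measures will be modeled using a covariance structure determined by information criteria (AIC/BIC").
- Site level: "Clinic site will be included as a random effect to account for site clustering". No site-by-time term is named.
- Small samples: "The Kenward-Rogers degrees of freedom correction will be used to account for a small number of clusters". No robust variance is planned for this model.

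Pain intensity, EQ-5D-5L, PSEQ, PCS, TSK-11 and PHQ-2 "will be analyzed using the same analytic approach as described for our primary LEFS analysis, adjusted for the same covariates".

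**The concern.** A cluster autocorrelation of 0.5 means that a site's mean moves between visits for reasons shared by its participants. A single site intercept treats the site effect as perfectly stable. A within-participant covariance, whichever structure AIC/BIC selects, cannot describe correlation between different participants at the same site and visit. Kenward-Roger corrects for few clusters only within the covariance that is fitted.

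The size of the error depends on a second point left open. Omitting the group main effect is the usual way to describe baseline means constrained equal across arms. With no baseline LEFS covariate, that constraint would be the only baseline adjustment. The remark that "Patient satisfaction and global rating of change do not include a baseline measure", given as the reason for a different model for those two outcomes, also suggests that baseline is part of the LEFS model. In SAS, however, time plus group-by-time with class variables leaves a free group difference at baseline unless baseline is explicitly excluded.

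At stake are the primary p-value and confidence interval and six further outcomes. The mediation analyses are also affected, because they run only if the intervention is judged effective. Chance drift at a few of the 14 sites could be reported as a treatment effect.

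**Working it through.** **Variance components, from Study Power.** Total 16² = 256.

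- Between-site: 0.1 × 256 = 25.6, split by the autocorrelation of 0.5 into site 12.8 and site-by-time 12.8.
- Within-site: 230.4, split by the individual autocorrelation of 0.6 into participant 138.24 and residual 92.16.
- Completers: 560 × 0.8 = 448, or 32 per site.

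**The plan's own figure.**

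- Design effect: 1 + (1.49 × 32 − 1) × 0.1 = 5.67.
- Correlation of site means between baseline and follow-up: r = (32 × 0.1 × 0.5 + 0.9 × 0.6) / (1 + 31 × 0.1) = 0.522.
- SE: √[(2 × 256/224) × 5.67 × (1 − 0.522²)] = 3.07.
- Power for 9 points: 83% with a normal reference, 77% with t on 12 df.

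So the stated power of more than 80% is reproduced with baseline adjustment and a normal reference, using an autocorrelation of 0.5.

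**Hand check, baseline constrained, equal sites.** The contrast is then largely the change from baseline to 12 months within sites.

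- True variance of a site's mean change: 2 × 12.8 + 2 × 92.16/32 = 31.4. SE of the arm difference: √(31.36 × 2/7) = 2.99.
- Site-only model, with site-by-time variance absorbed into the residual: 2 × (92.16 + 12.8)/32 = 6.56. SE: √(6.56 × 2/7) = 1.37.
- Ratio 2.99/1.37 = 2.2. The 1.96 threshold acts like about 0.90, giving a type I error of about 37%.

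**Hand check, baseline free, equal sites.** The contrast is largely between sites at 12 months.

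- True: 25.6 + 230.4/32 = 32.8. SE: √(32.8 × 2/7) = 3.06.
- Site-only: over five visits the site variance is estimated near 12.8 + 12.8/5 = 15.36, so 15.36 + (256 − 15.36)/32 = 22.88. SE: √(22.88 × 2/7) = 2.56.
- The SE is too small by a factor of about 1.2, so inflation is much milder.

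**Simulation.** REML with Kenward-Roger, null effect, five visits, complete data, no covariates, compound-symmetric participant covariance, 2,000 runs per case. CV 0.7 uses site sizes from 3 to 86, total 446.

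| Site sizes | Baseline | Model | Mean SE | Empirical SD | Type I error |
|---|---|---|---|---|---|
| CV 0.7 | constrained | site only | 1.34 | 3.25 | 42.6% |
| CV 0.7 | constrained | + site-by-time | 2.77 | 2.75 | 4.8% |
| CV 0.7 | free | site only | 2.66 | 3.40 | 11.0% |
| CV 0.7 | free | + site-by-time | 3.22 | 3.23 | 4.7% |
| Equal | constrained | site only | – | – | 35.4% |
| Equal | constrained | + site-by-time | – | – | 5.7% |
| Equal | free | site only | – | – | 10.7% |
| Equal | free | + site-by-time | – | – | 5.2% |

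At CV 0.7 the site-only model has a median of about 1,200 Kenward-Roger df when constrained and 14 when free.

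A separately coded simulation (1,000 to 1,500 runs per case) gave 36% to 49% constrained and 10% to 12% free across 32 to 52 participants per site, and 4.3% to 5.3% with the added term. A smaller one (300 runs per case), at a CV slightly above 0.7, gave 42–45% and 14–17%, and about 3–7% after the fix. An unstructured participant covariance does not help: 35.6% to 37% constrained with equal sites, and 45.0% at CV 0.7.

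**Sensitivity, site-only model, CV 0.7** (1,000 runs; other inputs as planned):

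| Assumption | Constrained | Free |
|---|---|---|
| Autocorrelation 0.8 | 24.5% | 7.1% |
| ICC 0.05 | 25.9% | 9.8% |
| ICC 0.02 | 14.8% | 7.3% |
| ICC 0.02 and autocorrelation 0.8 | 8.3% | – |
| Autocorrelation 1 | 5.5% | 6.1% |

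**The case against.** The strongest objection concerns the shape of the site effect. Follow-up is indexed to each participant's enrolment, and recruitment took 13 months, so one site's 12-month visits span more than a calendar year. Drift that follows calendar time partly averages out. With independent site-by-quarter shocks of variance 12.8, uniform enrolment and the site-only model (400 runs per case), type I error was 16.5% constrained and 7.0% free at CV 0.7, and 10.5% and 7.0% with equal sites.

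That scenario no longer has the planned correlations. Thirteen months is about 4.3 quarters, so two participants share a quarter at the same visit with probability of about 0.23. The same-visit covariance is then 12.8 + 0.23 × 12.8 = 15.7, giving an ICC of 15.7/256 = 0.06 and a visit-level autocorrelation of roughly 12.8/15.7 = 0.8. It is a milder input rather than a rebuttal, and it still shows inflation. Visit-indexed site effects are also plausible: there are seven physiotherapists at seven sites, treatment content is discretionary, and usual care is unstandardized.

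Other objections stand in part:

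- Sizing assumptions do not bind the analysis model, the ICC is described as conservative, and the plan does not exclude a site-by-time term. If the term was intended, the remedy is to write it down.
- The LEFS responder analysis uses a bias-corrected sandwich variance that does not assume an autocorrelation of 1. It is secondary and does not repair the primary test.
- The simulations omit covariates, attrition patterns and the constrained allocation, so the exact percentages are approximate.

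**Conclusion.** The concern holds. As written, the primary model gives standard errors that are too small under the plan's own planning values, whichever way baseline is handled. The figures of about 43% and 11% are conditional on ICC 0.1, cluster autocorrelation 0.5, site-size CV 0.7, a site effect shared at each visit, and a site intercept as the only site-level term. They are best read as the upper part of a range that narrows to about 8% (constrained) at ICC 0.02 with autocorrelation 0.8, and to about the nominal level at autocorrelation 1. True values are unknown until the data are analysed, which is why the model should estimate the component and not fix it at zero. This needs settling before the primary analysis is run.

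**What to change.** Before analysis starts:

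1. Add a site-by-time random effect alongside the site random effect in the primary LEFS model and in the six outcomes that share it, for example `RANDOM intercept time / SUBJECT=site TYPE=VC` with time as a class variable. Keep REML and Kenward-Roger. The AIC/BIC choice of participant covariance can stay.
2. State whether baseline means are constrained equal across arms, and code the model so that it does what is stated.

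If the added variance is estimated as zero, the model reduces to the current one.

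The work is two sentences and one model term. The statistical cost is wider intervals: at the planning values the mean SE rises from 1.34 to 2.77 (constrained) or from 2.66 to 3.22 (free). Power for 9 points at CV 0.7 with about 448 completers is then about 89% constrained, or about 78% free, the latter slightly below the stated figure of more than 80%. Analysis is due to begin only after data collection is complete, so the change can be made without sight of results.
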